As soon as possible after consent, the participant will participate in an in person visit for baseline biospecimen collection. On arrival, research staff wearing PPE will re-review the consent, confirm/obtain signatures, measure the PO2, do a urine pregnancy test in women with potential to be pregnant and measure the baseline QTc interval with the Kardia Mobile 6L (AliveCor, Inc). A 6 lead EKG is obtained when the patient places their fingers on 2 electrode sensors while holding

the device on their leg. The ECG is uploaded to an iPhone and the tracing is sent to the Electrophysiologist cardiologist who will calculate the QT and QTc. The device is approved by the FDA for QTc measurements. The participant will be excluded if the Q-T interval is prolonged beyond 450 Msec. We will also exclude anyone who has a PO2<92% or a positive pregnancy test. We will randomly allocate the participant, provide the assigned medications, and obtain mid-turbinate self nasal swab and blood samples. We will also take the participant's temperature and pulse. We will provide education to the patient on how to complete all at-home study procedures and use all ancillary study supplies which we will provide (self nasal swab specimen kits, thermometer, and pulse oximeter).

We will telephone the participant about 2 hours after the initial medication dose to confirm that the Zio AT patch has been triggered for the one-time 2 hour reading (see the Risks of Harm/Potential for Benefits to Subjects to Subjects section, page 35), review the BID dosing schedule, study procedures, and any participant questions. We will also call on days 3, 6, and 10 for procedure review and to confirm self- specimen collection and AE review. We will have an in person visit on day 14 to collect a blood specimen and on day 28 to collect a blood specimen and urine pregnancy test, review medical status and AEs Self collection of mid-turbinate nasal swab to measure viral shedding will be on days 3, 6 and10 post randomization.

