1.6 Study Variables

A. Primary Outcome:

Viral load at 10 days post randomization

B. Other measures

Age, Gender Race/ethnicity BMI Co-morbidity:

- Diabetes mellitus
- Hypertension
- Chronic bronchitis, emphysema, or chronic obstructive pulmonary disease (COPD)
- Other lung disease
- Coronary artery disease, peripheral artery disease, angina, or heart attack (myocardial infarction)
- Congestive heart failure
- Stroke or transient ischemic attack (TIA)
- Atrial fibrillation
- Cancer other than non-melanoma skin cancer
- Chronic kidney disease (CKD)
- Crohn's disease, ulcerative colitis, or inflammatory bowel disease (IBD)
- Rheumatoid arthritis (RA), psoriasis, systemic lupus, multiple sclerosis, or another autoimmune disorder
- Allergic rhinitis

Medications Symptoms Household infection (confirmed or suspected)

List variables of interest

Treatment Variables:

- Treatment Compliance
- Adverse Events (number/percentage/grade)

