Availability: FDA approved; commercially available hydroxychloroquine sulfate will be supplied free of charge to all patients enrolled.

[figure not shown]
Generic name: Ribavirin Commercial name:

For complete information please refer to the package inserts at http://dailymed.nlm.nih.gov/dailymed/ribavirin

Chemical name: 1-β-Dribofuranosyl-1H-1,2,4-triazole-3-carboxamide

Source: Commercially available

 $C_8 H_{12} N_4 O_5$ and the molecular weight is 244.2

Ribavirin, USP is white, crystalline powder. It is freely soluble in water and slightly soluble in dehydrated alcohol. Each film-coated ribavirin tablet intended for oral administration contains 200 mg or 400 mg or 500 mg or 600 mg of ribavirin. In addition, each tablet contains the following inactive ingredients: crospovidone, hypromellose, iron oxide red, iron oxide yellow, magnesium stearate, microcrystalline cellulose, polyethylene glycol, povidone, silicon dioxide, talc, and titanium dioxide.

Pharmacokinetics

Multiple dose ribavirin pharmacokinetic data are available for HCV patients who received ribavirin in combination with peginterferon alfa-2a. Following administration of 1200 mg/day with food for 12 weeks mean±SD (n=39; body weight greater than 75 kg) AUC was 25,361±7110 ng·hr/mL and C was 2748±818 ng/mL. The average time to reach C was 2 hours. Trough ribavirin plasma concentrations following 12 weeks of dosing with food were 1662±545 ng/mL in HCV infected patients who received 800 mg/day (n=89), and 2112±810 ng/mL in patients who received 1200 mg/day (n=75; body weight greater than 75 kg). The terminal half-life of ribavirin following administration of a single oral dose of ribavirin is about 120 to 170 hours. The total apparent clearance following administration of a single oral dose of ribavirin is about 26 L/h. There is extensive accumulation of ribavirin after multiple dosing (twice daily) such that the C at steady state was four-fold higher than that of a single dose.

Contraindications:

Ribavirin

Pregnancy: Women who are or may become pregnant. Ribavirin may cause fetal harm when administered to a pregnant woman. women who are or may become pregnant. If this drug is used during pregnancy, or if the patient becomes pregnant while taking this drug, the patient should be apprised of the potential hazard to the fetus Men whose female partners are pregnant.

Hemoglobinopathies: Patients with hemoglobinopathies (e.g., thalassemia major or sickle-cell anemia).

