The participant will then come to the study location at [name] to complete final screening for the trial eligibility. P02 will be measured and 6 lead portable electrocardiogram will be performed; if PO2<92% or QT interval is QTc interval > 450 mSEC the participant will be excluded. Females of childbearing potential will have a urine test to confirm that they are not pregnant.

Inclusion Criteria

- 1. Documented SARS-CoV-2 infection by qPCR assay without symptoms or with mild symptoms consistent with COVID-19 performed within the past 7 days
- 2. Age ≥21

Exclusion Criteria

- 1. COVID-19 symptoms requiring hospitalization
- 2. PO2 < 92%
- 3. Short of breath at time of enrollment
- 4. Retinal eye disease
- 5. Known glucose-6 phosphate dehydrogenase (G-6-PD) deficiency
- 6. Known chronic kidney disease, stage 5 or receiving dialysis
- 7. Current use of:
 - Class 3 AAD (amiodarone, dronaderone, dofetilide, sotalol)
 - Class 1A AAD (procainamide, quinidine, disopyramide)
 - Flecainide
 - SSRI: citalopram (Celexa), Escitalopram (Lexapro)
 - chlorpromazine
 - Cilostazol (Pletal)
 - Donepezil (Aricept)
 - Droperidol
 - Fluoconazole
 - Methadone
 - Ondansetron (Zofran)
 - Thioridazine
 - Macrolides (clarithromycin, erythromycin)
 - Fluroquinolones (ciprofloxacin, levofloxacin, moxifloxacin)
 - Tamoxifen citrate
- 8. Pregnancy or women who are breast feeding
- 9. Inability to tolerate oral medications
- 10. Allergy or prior adverse reaction to either hydroxychloroquine sulfate, ribavirin, or nitazoxanide
- 11. Allergy to adhesives
- 12. QTc interval > 450 mSEC for men and women
- 13. History of Torsade de Pointes VT or prior cardiac arrest or congenital long QT interval
- 14. Non-English-speaking

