Females of childbearing potential should use reliable methods of contraception from the time of screening until 6 months after discontinuing study treatment. Acceptable methods of contraception include abstinence, tubal ligation, combined oral, transdermal, or intra-vaginal hormonal contraceptives, medroxyprogesterone injections (e.g., Depo-Provera), copper-banded intra-uterine devices, hormone impregnated intra-uterine systems and vasectomised partners. All methods of contraception (except for total abstinence) should be used in combination with the use of a condom by their male sexual partner for intercourse.

Males

Male patients must use a condom during sexual intercourse with all sexual partners including a pregnant female partner during the study and for 4 weeks after discontinuing study treatment. However, where a sexual partner of a male participant is a woman of childbearing potential who is not using effective contraception, men must use a condom during sexual intercourse during the; study and for 6 months after discontinuing study treatment. Male patients should avoid procreation during the trial and for 6 months after discontinuing study treatment.

C. Risks of Harm to Non-Participants

When evaluating the patient during the visit, research personnel will wear appropriate personal protective equipment (PPE) as recommended by the CDC. This includes the following:

- Gown
- Gloves
- Eye/face protection (i.e., goggles, face shield)
- If available, National Institute for Occupational Safety and Health (NIOSH)-certified disposable N95 or better respirator. The CDC has stated that surgical (face) masks have been determined to be an acceptable alternative to N95 or better respirators, when the supply chain of respirators cannot meet the demand so long as procedures that are likely to generate respiratory aerosols are not being performed. The use of mid-turbinate nasal swabs to collect viral load specimens during this study is not considered an aerosolizing procedure.

D. Assessment of Social Behavior Considerations N/A

E. Minimizing Risks of Harm

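### Two ribavirin contraindications that the protocol itself lists, a pregnant female partner and hemoglobinopathy, have no matching exclusion, and the condom rule conflicts with the first

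*Combined protocol and SAP*

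**What the plan says.** Section 1.7 (Ribavirin, Contraindications) names, besides women who are or may become pregnant, two further groups: "Men whose female partners are pregnant" and "Patients with hemoglobinopathies (e.g., thalassemia major or sickle-cell anemia").

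Section 4.1 C has 14 numbered exclusions. The only one about pregnancy is no. 8, "Pregnancy or women who are breast feeding". The only one about a blood disorder is no. 5, known G-6-PD deficiency. The only one that names ribavirin is no. 10, which covers allergy or a previous adverse reaction.

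Section 1.3 B describes the baseline visit. It excludes a prolonged QT interval and then adds: "We will also exclude anyone who has a PO2<92% or a positive pregnancy test". The pregnancy test is the participant's own.

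Section 4.7 B (Males) addresses a partner who is already pregnant: "Male patients must use a condom during sexual intercourse with all sexual partners including a pregnant female partner". This applies during the study and for 4 weeks afterwards. The same paragraph adds: "Male patients should avoid procreation during the trial and for 6 months after discontinuing study treatment".

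**The concern.** The eligibility list is what staff apply at enrolment. If the drug section says a person must not take ribavirin and the list does not stop that person, someone can be enrolled correctly under section 4.1 C and still be given a contraindicated drug. Because treatment is masked, staff would not know which of these participants was taking ribavirin.

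The stakes differ between the two groups. For the pregnant partner, the harm would fall on a fetus, a third party outside the trial. The section 1.7 warnings report teratogenic or embryocidal effects in every animal species adequately studied, at doses down to one twentieth of the human dose. For hemoglobinopathy, the concern is hemolytic anemia in people whose red cells are already abnormal.

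**Working it through.** The plan states no figure to reproduce. The check compares the contraindications with the eligibility text and adds two short sums.

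**1. Contraindications against eligibility text**

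| Ribavirin contraindication (1.7) | 14 exclusions (4.1 C) | Baseline-visit checks (1.3 B) | Elsewhere |
|---|---|---|---|
| Man with a pregnant partner | 0 match; no. 8 concerns the participant only | None; the test is the participant's own | 4.7 B: condoms, with no bar to dosing |
| Hemoglobinopathy | 0 match; no. 5 is an enzyme defect | None | Not found |

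**2. Is there a catch-all?** No. Exclusion 10 and the opening of section 1.3 cover allergy, intolerance or a prior reaction. Section 4.1 C has no clause on contraindications to study drugs, no investigator-discretion clause and no hemoglobin threshold.

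**3. Does the baseline blood count act as a screen?** Section 1.3 A places the blood draw, randomisation and dispensing at the same visit and allows the first dose that day. No result has to be seen before dosing, and no value leads to exclusion. The count is therefore a baseline measurement and does not control entry.

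**4. Do sections 1.7 and 4.7 B agree?** They do not. Section 1.7 says a man with a pregnant partner should not take ribavirin. Section 4.7 B tells him to take precautions while he is in the study. Neither section refers to the other, and no reason is given for departing from the contraindication.

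**5. Were other drug warnings turned into exclusions?** Yes. For hydroxychloroquine, section 1.7 advises only caution in G-6-PD deficiency and names tamoxifen as a retinal risk factor. Both appear in the exclusions (nos. 5 and 7). The two ribavirin items are worded more strongly and do not appear.

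**6. Exposure of a person enrolled**

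- Dose (1.3 A, Treatment Plan): 1,200 mg on day 1, then 800 mg daily for 4 days. 1,200 + 4 × 800 = 4,400 mg.
- Chance of the active arm (1.5): 35 of 70. 35/70 = 0.50.

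**The case against.** The strongest reply is that the protocol foresaw the pregnant partner and chose a different control. Section 4.7 B names the case, and the same section requires counselling on reproductive toxicity through the consent form. The contraindication list is also not applied line by line: it bars women who may become pregnant, yet the trial enrols women of childbearing potential who use contraception. This shows that the case was not overlooked. It does not settle the conflict, because contraception prevents a pregnancy and cannot help when one already exists.

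Second, the online screening questionnaire is not reproduced, and a medical history is taken at baseline, so staff may in practice learn of either condition. That is possible, but section 4.1 C would give them no criterion on which to exclude the person.

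Third, the anemia risk is probably small. Section 4.7 E ties hemolysis to long-term use, section 1.2 reports no significant hemoglobin fall in short courses, and the 13% in section 1.7 comes from treatment with peginterferon. This stands, and it makes hemoglobinopathy the weaker of the two gaps. It does not close the gap, because the documents do not say that the short-course studies included people with hemoglobinopathies, and the contraindication is not limited by duration.

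A reader might also draw two stronger inferences:

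- **That the hemoglobin checks come too late.** Section 1.7 says the anemia appears within 1 to 2 weeks and advises testing before treatment and at weeks 2 and 4. Baseline, day 14 and day 28 follow that advice.
- **That cardiac disease is a third missed contraindication.** The sentence saying that people with significant or unstable cardiac disease should not use ribavirin is a warning, and its terms are undefined. The same paragraph allows pre-existing cardiac disease with an ECG and monitoring. The trial provides a 6-lead ECG, telemetry and rhythm exclusions such as "History of Torsade de Pointes VT or prior cardiac arrest or congenital long QT interval". Recording "Coronary artery disease, peripheral artery disease, angina, or heart attack (myocardial infarction" as a comorbidity in section 1.6 is compatible with that.

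**Conclusion.** The point holds for two groups. Two contraindications listed in section 1.7 have 0 matches among 14 exclusions and none among the baseline-visit checks. For one of them, section 4.7 B contradicts section 1.7. Each such person enrolled has a 50% chance of receiving 4,400 mg of ribavirin.

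How many people this would affect cannot be stated. The documents give no prevalence for either group, so a reader who infers that exposure is likely, or that it is negligible, goes beyond them. The conclusion does not depend on prevalence, because it concerns what the written criteria allow.

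The fetal concern carries most of the weight. This is a participant-safety correction to be made before enrolment, with no bearing on the estimand, power or analysis. It rests on section 4.1 C being the complete eligibility list, which its numbering from 1 to 14 supports, and on no unreproduced document adding a binding criterion.

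**What to change.** 1. Add two exclusions to section 4.1 C: a male participant whose female partner is pregnant, and known hemoglobinopathy, with thalassemia major and sickle-cell anemia as examples.
2. Ask about both at screening, and check that the online questionnaire includes them.
3. In section 4.7 B, limit the pregnant-partner condom rule to pregnancies discovered after enrolment, so that it no longer conflicts with section 1.7.

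Minor and optional: add didanosine to exclusion 7, since the section 1.7 contraindications also name that combination. The study cardiologist could also confirm at baseline that the participant has no significant or unstable cardiac disease, which would give the undefined warning in sections 1.7 and 4.7 A a working meaning.

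The cost is an amendment to the eligibility list, a questionnaire check, an edit to one paragraph, and the loss of a few otherwise eligible volunteers. These exclusions apply before randomisation, so the target of 70 and the analysis stay as they are.

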1.3 Research Design and Methods

We will conduct a randomized clinical trial enrolling eligible participants who are determined to be SARS-CoV-2-positive (e.g., via Rutgers Corona Cohort [RCC] study, hospital or other screening programs) who volunteer for the study. Specifically, we will enroll 70 participants whose test has been performed within the past 7 days who are either asymptomatic or mildly symptomatic at baseline. Mild COVID-19 symptoms include new cough, sore throat, fever, myalgias, new vomiting or diarrheaor change in smell or taste. Illness requiring hospitalization, or those who present with hypoxia (PO2<92%) or shortness of breath at time of enrollment will be classified as significantly symptomatic and excluded from study participation. People who are allergic or intolerant to NTZ, RBV or HCQ will be excluded. We will randomly allocate participants stratified by presence of mild symptoms to 1) NTZ, RBV and HCQ or 2) placebo. Treatment with the investigational agents or placebo will continue for 5 days. Viral load will be assessed at baseline (day 0) as well as at days 3, 6, and 10 to monitor response to antiviral treatment. Immune status will be determined by antibody testing of blood collected at baseline and day 28.

Prior to initiating enrollment, we will prepare two randomization tables for treatment assignment using permuted blocks of six which will be provided to the research pharmacist. One table will be used for participants without symptoms and the other will be used for those with mild symptoms. The pharmacist will prepare kits containing the 5-day supply of study medications (investigational drugs/placebo) which will be sequentially numbered in accordance with the randomization tables. The contents of each kit (investigation drugs/placebo) will be indistinguishable. Study staff will establish symptom status at the baseline visit, and per pharmacy order, provide the participant the next numbered medication kit in the participant's stratum (no symptoms/mild symptoms). The study investigators, staff interacting with the participants are all masked to treatment assignment

A. Research Procedures

- 1. Study Procedures:
 - Day 0/1 Screening/Baseline Visit (in person)
 - Pre-screen via online screening form to confirm eligibility
 - Obtain informed consent for trial enrollment
 - Medical history
 - Medication history
 - Document symptoms (if any)

- o Take temperature, PO2, Pulse
- Q-T interval assessment

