 - Arm 1: NTZ 1000 mg (2 x 250 mg tablets BID for day one) and then 1000 mg (2 x 250 mg tablets BID for 4 days) RBV 1200 mg (3 x 200 mg capsules BID day one) and then RBV 800 mg (2 x 200mg capsules BID for 4 days) HCQ 800 mg (2 x 200 mg tablets bid day one) and then HCQ 400 mg (1 x 200 mg tablet BID for 4 days)
 - Arm 2: Placebo for NTZ (2 tablets BID for day one and then 2 tablets BID for 4 days) Placebo for RBV (3 capsules BID day one and then 2 capsules BID for 4 days) Placebo for HCQ (2 tablets bid day one and then 1 tablet BID for 4 days)

Hydroxychloroquine sulfate (HCQ)

One hydroxychloroquine sulfate tablet contains 200 mg of hydroxychloroquine sulfate, which is the equivalent to 155 mg base.

Ribavirin (RBV)

One ribavirin capsule contains 200 mg of ribavirin.

Nitazoxanide (NTZ)

One nitazoxanide tablet contains 500 mg of nitazoxanide.

Take all tablets/capsules with a meal or a glass of milk.

All study drugs should be stored at room temperature 20°-25° (68°-77 °F).

Concomitant Medications & Supportive Guidelines

Study participants can receive full supportive care therapies concomitantly during the study. We will advise rest, fluids, hot/ showers/baths. We will recommend NO antipyretics since they make infections worse by interfering with the generation of fever--which is considered beneficial until it reaches 102 degrees F.

B. Participant Enrollment

We will identify asymptomatic or mildly symptomatic participants who test positive for SARS-CoV-2 from the Rutgers Coronavirus Cohort (RCC) and hospital screening programs, or from the community through advertisements at our medical center, university, and in local publications. The recruiting materials will direct the potential participants to online materials that include information about the trial, consent forms, and a screener questionnaire to assess eligibility. If eligible for the trial, we will answer any questions and provide as much time as needed to review all study materials. The participant may then electronically sign the consent or, as an alternative, wait until the initial visit to re-review and sign the consent. The consenting process will be primarily performed remotely to protect research personnel.

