Cardiac Effects, including Cardiomyopathy and QT prolongation: Post-marketing cases of life-threatening and fatal cardiomyopathy have been reported with use of hydroxychloroquine sulfate as well as with use of chloroquine. Hydroxychloroquine sulfate prolongs the QT interval. Ventricular arrhythmias and torsades de pointes have been reported in patients taking hydroxychloroquine sulfate (see OVERDOSAGE). Therefore, hydroxychloroquine sulfate should not be administered with other drugs that have the potential to prolong the QT interval.

Worsening of psoriasis and porphyria

Proximal Myopathy and Neuropathy

Neuropsychiatric events, including suicidality

Hypoglycemia: Hydroxychloroquine sulfate has been shown to cause severe hypoglycemia including loss of consciousness that could be life threatening in patients treated with or without antidiabetic medications

General precautions: General: Use with caution in patients with gastrointestinal, neurological, or blood disorders, and in those with a sensitivity to quinine.

Hepatic/Renal Disease: Antimalarial compounds should be used with caution in patients with hepatic disease or alcoholism or in conjunction with known hepatotoxic drugs. A reduction in dosage may be necessary in patients with hepatic or renal disease, as well as in those taking medicines known to affect these organs.

Hematologic Effects/Laboratory Tests: Antimalarial compounds should be used with caution in patients with hepatic disease or alcoholism or in conjunction with known hepatotoxic drugs. Periodic blood cell counts should be performed if patients are given prolonged therapy.

Hydroxychloroquine sulfate should be administered with caution in patients having glucose-6-phosphate dehydrogenase (G-6-PD) deficiency.

Dermatologic Effects: Dermatologic reactions to hydroxychloroquine sulfate may occur and, therefore, proper care should be exercised when it is administered to any patient receiving a drug with a significant tendency to produce dermatitis.

Drug Interactions (include but not limited to): Digoxin, Insulin or antidiabetic drugs, Drugs that prolong QT interval and other arrhythmogenic drugs, Mefloquine and other drugs known to lower the convulsive threshold, Antiepileptics, Methotrexate, Cyclosporin, Praziquantel, Antacids and kaolin, Cimetidine, Ampicillin.

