The primary toxicity of ribavirin is hemolytic anemia, which was observed in approximately 13% of all ribavirin/peginterferon alfa-2a- treated participants in clinical trials. Anemia associated with ribavirin occurs within 1 to 2 weeks of initiation of therapy. Because the initial drop in hemoglobin may be significant, it is advised that hemoglobin or hematocrit be obtained pretreatment and at week 2 and week 4 of therapy or more frequently if clinically indicated. Patients should then be followed as clinically appropriate. Caution should be exercised in initiating treatment in any patient with baseline risk of severe anemia (e.g., spherocytosis, history of gastrointestinal bleeding). Fatal and nonfatal myocardial infarctions have been reported in patients with anemia caused by ribavirin. Patients should be assessed for underlying cardiac disease before initiation of ribavirin therapy. Patients with pre-existing cardiac disease should have electrocardiograms administered before treatment and should be appropriately monitored during therapy. If there is any deterioration of cardiovascular status, therapy should be suspended or discontinued. Because cardiac disease may be worsened by drug-induced anemia, patients with a history of significant or unstable cardiac disease should not use ribavirin.

Hepatic Failure

Chronic hepatitis C (CHC) patients with cirrhosis may be at risk of hepatic decompensation and death when treated with alpha interferons, including peginterferon alfa-2a. Cirrhotic CHC patients coinfected with HIV receiving highly active antiretroviral therapy (HAART) and interferon alfa-2a with or without ribavirin appear to be at increased risk for the development of hepatic decompensation compared to patients not receiving HAART.

Hypersensitivity

Severe acute hypersensitivity reactions (e.g., urticaria, angioedema, bronchoconstriction, and

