The primary toxicity of Ribavirin is hemolytic anemia, which was observed in approximately 13% of all Ribavirin/peginterferon alfa-2a- treated participants in clinical trials. Anemia associated with Ribavirin occurs within 1 to 2 weeks of initiation of therapy. Because the initial drop in hemoglobin may be significant, it is advised that hemoglobin or hematocrit be obtained pretreatment and at week 2 and week 4 of therapy or more frequently if clinically indicated. Patients should then be followed as clinically appropriate. Caution should be exercised in initiating treatment in any patient with baseline risk of severe anemia (e.g., spherocytosis, history of gastrointestinal bleeding)

Fatal and nonfatal myocardial infarctions have been reported in patients with anemia caused by Ribavirin. Patients should be assessed for underlying cardiac disease before initiation of Ribavirin therapy. Patients with pre-existing cardiac disease should have electrocardiograms administered before treatment and should be appropriately monitored during therapy. If there is any deterioration of cardiovascular status, therapy should be suspended or Because cardiac disease may be worsened by drug-induced anemia, patients with a history of significant or unstable cardiac disease should not use Ribavirin.

Hepatic Failure

Chronic hepatitis C (CHC) patients with cirrhosis may be at risk of hepatic decompensation and death when treated with alpha interferons, including peginterferon alfa-2a. Cirrhotic CHC patients coinfected with HIV receiving highly active antiretroviral therapy (HAART) and interferon alfa-2a with or without Ribavirin appear to be at increased risk for the development of hepatic decompensation compared to patients not receiving HAART. In Study NR15961 among 129 CHC/HIV cirrhotic patients receiving HAART, 14 (11%) of these patients across all treatment arms developed hepatic decompensation resulting in 6 deaths. All 14 patients were on NRTIs, including stavudine, didanosine, abacavir, zidovudine, and lamivudine. These small numbers of patients do not permit discrimination between specific NRTIs or the associated risk. During treatment, patients' clinical status and hepatic function should be closely monitored for signs and symptoms of hepatic decompensation. Treatment with peginterferon alfa-2a/Ribavirin should be discontinued immediately in patients with hepatic decompensation.

Hypersensitivity

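### The warning against ribavirin in significant or unstable cardiac disease reaches the exclusion list only in part: ischemic disease and heart failure are not covered

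*Combined protocol and SAP*

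**What the plan says.** Section 1.7, under the ribavirin warnings on anemia, gives three instructions. Patients are to be assessed for heart disease before starting. Those with existing disease are to have an ECG and suitable monitoring. In the serious tier, "patients with a history of significant or unstable cardiac disease should not use ribavirin". Section 4.7 A repeats this with its reason: "Because cardiac disease may be worsened by drug-induced anemia, patients with a history of significant or unstable cardiac disease should not use Ribavirin". Both sections report fatal and nonfatal infarctions in patients whose anemia was caused by ribavirin.

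Section 4.1 C lists 14 exclusions. The one closest to the warning is item 13: "History of Torsade de Pointes VT or prior cardiac arrest or congenital long QT interval". Item 7 removes current users of listed drugs, among them several antiarrhythmics, and item 12 removes anyone with QTc above 450 msec. Item 1 is limited to "COVID-19 symptoms requiring hospitalization".

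Section 1.6 B lists coronary disease, angina, infarction and heart failure as co-morbidities to record. The active arm's ribavirin dosing in Section 1.3 is fixed: "RBV 1200 mg (3 x 200 mg capsules BID day one) and then RBV 800 mg" per day for the remaining 4 days. Section 4.7 E schedules hemoglobin at baseline, day 14 and day 28.

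**The concern.** The protocol names a group that should not receive one of its three drugs, but its eligibility rule does not keep that whole group out. The cardiac exclusions that exist are aimed at QT prolongation and arrhythmia. The ribavirin warning rests on a different mechanism: anemia placing strain on a diseased heart. Ischemic disease and heart failure are the conditions most exposed to that mechanism, and no criterion names them.

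The participants are asymptomatic or mildly ill volunteers, aged 21 or over with no upper limit, recruited in part by public advertisement. The outcome warned of includes fatal infarction. Sections 1.4 and 1.7 add that there is no human experience with the triple combination and no data on its combined risk.

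**Working it through.** The main check is a comparison of texts; the arithmetic is short.

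**1. Each exclusion against the warning**

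| Item in Section 4.1 C | What it removes | Bearing on the warning |
|---|---|---|
| 1 | COVID-19 symptoms needing hospital care | None on cardiac history |
| 2, 3 | PO2 below 92%; breathlessness at enrollment | Removes some decompensated patients on the day, not a history |
| 7 | Current users of listed drugs | Part of the arrhythmia group |
| 12 | QTc above 450 msec | QT risk |
| 13 | Torsade, prior cardiac arrest, congenital long QT | Rhythm and arrest subset |
| 4, 5, 6, 8, 9, 10, 11, 14 | Retinal disease, G-6-PD deficiency, end-stage kidney disease, pregnancy or breast feeding, oral intolerance, drug allergy, adhesive allergy, language | None |

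Three of the 14 (items 7, 12 and 13) cover a QT or arrhythmia subset. None names ischemic disease or heart failure, and none leaves eligibility to the investigator's discretion. The eligibility statements in Sections 1.1, 1.3, 4.1 A and 4.7 B add no cardiac criterion beyond the QT limit.

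**2. A test case.** Take a 60-year-old with a positive qPCR in the past 7 days, a recent infarction, no breathlessness, PO2 of at least 92%, QTc of 450 msec or less, no listed drug and no other exclusion. Both inclusion criteria are met and no exclusion applies, so the person can be randomized. Past decompensated heart failure without breathlessness on the day gives the same result.

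**3. Exposure if assigned to active treatment** (Section 1.3)

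1,200 mg + 4 × 800 mg = 4,400 mg over 5 days.

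**4. What can act, and when**

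- Before dosing: baseline ECG, medical history and blood count.
- During dosing: telemetry through day 10, with a stopping rule for a QT increase above 60 msec or QT above 500 msec.
- After dosing: first follow-up hemoglobin on day 14. With the last dose on day 5, the gap is 14 − 5 = 9 days.

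ECG and telemetry meet the warning's monitoring tier. They do not meet its should-not-use tier. The day 14 hemoglobin comes too late to stop the drug for anemia that the drug has caused.

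**5. How the plan treats other conditions.** On G-6-PD deficiency, Section 1.7 asks only for care: "Hydroxychloroquine sulfate should be administered with caution in patients having glucose-6-phosphate dehydrogenase (G-6-PD) deficiency". The plan made this exclusion 5: "Known glucose-6 phosphate dehydrogenase (G-6-PD) deficiency". Chronic kidney disease is a recorded co-morbidity in Section 1.6 B, yet its severe tier is exclusion 6. Recording a condition and excluding its serious tier therefore already coexist in this plan.

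**The case against.** The strongest objection is that the anemia premise is weak for a 5-day course. The 13% anemia figure in Section 1.7 comes from ribavirin with peginterferon. Section 4.7 E ties hemolytic anemia to long-term use, and Section 1.2 reports no significant hemoglobin decrease in short courses. The COVID-19 trial cited there planned 2 × 400 mg × 14 days = 11,200 mg, and 11,200 / 4,400 = 2.55 times this course. This stands, and it lowers the expected risk. It does not set the warning aside. The documents do not say whether that trial enrolled people with serious heart disease, and Section 4.7 A repeats the warning without qualification.

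A second objection is that clinicians may catch these patients anyway. Section 1.7 calls for cardiac assessment before ribavirin, medical history is taken at baseline, and Section 1.7 B refers to the treating investigator's instructions. An investigator could decline to dose. The screening questionnaire is not in the documents, so its content cannot be judged. But the described screening steps give no rule for acting on such a history, and the exclusion list would pass the patient.

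Several stronger readings are tempting but unsupported:

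- A reader might infer that the list ignores cardiac disease altogether. It does not: items 7 and 13 remove part of the group, and prior cardiac arrest is serious heart disease on any reading.
- A reader might call this a breached contraindication. Section 1.7 places it under warnings, not among the listed contraindications.
- A reader might infer that anemia would appear only after dosing. Section 1.7 gives 1 to 2 weeks as an outer limit, not a delayed onset.
- A reader might fault the hemoglobin schedule. It matches the week 2 and week 4 checks in the warning, and the baseline count is also a scheduled result that could prompt a stop. Only the day 14 result comes too late.
- A reader might take active unstable angina as plainly eligible. That is less clear. Section 1.3 says "Illness requiring hospitalization, or those who present with hypoxia (PO2<92%) or shortness of breath at time of enrollment will be classified as significantly symptomatic", which can be read to cover any illness, whereas exclusion 1 is confined to COVID-19.

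The G-6-PD comparison concerns another drug and another hazard. It shows how the plan handled a milder caution; it does not by itself prove an error.

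**Conclusion.** The concern holds as a partial gap. The eligibility rule admits some people whom the protocol itself says should not take ribavirin, chiefly those with serious ischemic disease or heart failure who are not breathless or hypoxic and whose QTc is within the limit. No other section screens them out or waives the warning.

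The size cannot be given as a number of participants or a probability of harm. The documents give neither the prevalence of such disease nor an infarction rate for a 5-day course. What can be said is that about 35 of the 70 participants are planned for active treatment, each assigned 4,400 mg of ribavirin, with the first follow-up hemoglobin 9 days after the last dose. The conclusion rests on reading the 14-item list as complete and on no unseen questionnaire item acting as an exclusion. It is worth correcting because the change is cheap and the outcome warned of is grave, not because harm has been shown to be likely.

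**What to change.** Add one exclusion to Section 4.1 C: a history of significant or unstable cardiac disease, for example recent myocardial infarction, unstable angina, or decompensated or symptomatic heart failure. The study cardiologist should set the time window and final definition before enrollment. Ask about it in the online screening questionnaire and confirm it in the baseline medical history, before randomization. Stable cardiac disease stays eligible under the existing ECG and telemetry.

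The cost is one line and one screening question, on conditions that Section 1.6 B already collects. No assumption in the Section 1.5 power calculation changes. A few volunteers will be lost; the number is unknown because no prevalence is given. The check will rest on self-report, since Section 1.9 B rules out abstracting records on previous health history. Some clinical judgment about what counts as significant will remain, but it will be exercised against a written definition.
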